first we will use fMRI to investigate neural correlates of lower limb control with a foot-tapping task under IG and EG conditions in veterans with and without PD (Aim 1). Imaging studies have previously employed foot-tapping, which is used clinically to assess lower limb control. To achieve Aim 2, we will 1) evaluate the relative effectiveness of practicing IG movement (leading) versus practicing EG movement (following) versus a behavioral control (health education) for improved mobility and lower limb control, and 2) assess neural activity changes underlying improvements in lower limb control across training groups. The long-term goal is to optimize motor rehabilitative interventions for veterans with PD and understand the neural mechanisms through which the training is effective in order to further improve rehabilitation strategies for this and similar diseases.

**Specific Aim 1: Determine neural correlates of internally guided and externally guided foot-tapping in individuals with and without PD.**

**Hypothesis 1:** In healthy controls, IG and EG foot-tapping are related to task-specific neural networks of the striato-thalamo-cortical and cerebello-thalamo-cortical circuits, respectively. In those with PD relative to controls, IG foot-tapping will result in increased activation of both the STC (posterosuperior putamen, ventral anterolateral thalamus, rostral supplementary motor area, primary motor cortex) and the CTC (cerebellum (Larsell lobules IV, V, and VI), ventral posterolateral thalamus, primary somatosensory cortex, ventral premotor cortex) circuits. EG foot-tapping will result in increased activation in the CTC circuit only.

**Specific Aim 2: Determine the effect, in individuals with PD, of internally guided versus externally guided training compared to a behavioral control on: 1) mobility, and 2) whether improved mobility and foot-tapping performance after training correlate with changes in activation and resting-state functional connectivity patterns in IG and EG foot-tapping networks.**

**Hypothesis 1:** If mobility gains are related to training in planning and selecting movements, then those in IG will demonstrate greater improvements than those in EG or control. If mobility gains are related to exploiting cues during training, then those in EG will demonstrate greater improvements than those in IG or control.

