### **Statistical Analysis Plan for Aim 1**

- **Participant characteristics:** Descriptive statistics will describe groups, including disease severity and duration for those with PD. T-tests will compare means (e.g., age, mental status) of participants with and without PD. Data analyses will be completed in SPSS (v. 19).
- **Functional performance measures:** Foot-tapping absolute timing error and average amplitude will be compared between groups with t-tests. These measures will also be correlated to fMRI data.
- **fMRI Brain Activation Analyses:** Following preprocessing and normalization to standard space, activation maps for the IG and EG tasks versus rest will be determined for each subject on a voxel by voxel basis. Regressors of interest will model IG and EG blocks of foot movement for each limb separately. Head motion parameters will be included as additional regressors. A similar approach has been used previously in PD. First level contrast maps (betas) for the IG and EG tasks versus rest derived in each subject will be submitted to a second-level, random-effects analysis with subject as a random factor. Second-level t-maps will be thresholded at  $p <.05$ , corrected for multiple comparisons using the false discovery rate (FDR) method. These activation maps will be used to define circuitry for IG and EG foot-tapping. Average percent signal change for the IG and EG tasks (relative to rest) for each participant will be extracted from the centers of gravity of the activated regions and submitted to hierarchical regression analyses to determine whether they correlate with behavioral measures (absolute timing errors and average amplitude of foot-tapping). Disease severity and duration of illness will be covariates for individuals with PD. **The primary outcome measure will be average percent signal change** for the IG and EG tasks (relative to

rest) to determine and distinguish circuits involved in IG and EG foot-tapping networks in participants with and without PD.

## Power Analyses for Aim 2

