## Statistical Analysis Plan for Aim 2, Hypothesis 1, 2 and 3:

- **Participant demographics:** Descriptive statistics will characterize groups. One-way ANOVA will determine differences, if any, between groups on baseline measures.
- **Behavioral Outcome measures:** A 3 group (IG, EG, BC) x 3 time (pre, post test, follow-up (1-month later)) RM ANOVA will be used to detect main effects. Appropriate post hoc tests will be used to determine within- and between-group differences,  $p<0.05$ , for **BBS, the primary outcome** measure upon which Aim 2 is powered. Statistical tests run on all secondary variables will be corrected for multiple comparisons.
- **Brain Activation Analyses for Aim 2, Hypothesis 2:** Similar to Aim 1 procedures, average percent signal change for IG and EG tasks (relative to baseline) for each participant will be extracted from the centers of gravity of the activated regions and submitted to hierarchical regression analyses to determine whether they correlate with behavioral measures (foot-tapping absolute timing errors and average amplitude). Disease severity and PD duration will be covariates. To determine the effects of time and training status we will submit the percent signal change to a 3 group (IG, EG and BC) X 2 time (pre, post) RM ANOVA. Post-hoc analyses will be corrected for multiple comparisons. The **primary outcome** will be t-contrast maps and effect size maps from ANOVA, which will be evaluated for changes in STC and CTC circuits.

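### Aim 1 takes its signal-extraction locations from each task's own activation map, so the IG-versus-EG comparison is circular; PD versus control is circular only if maps are made per group

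*Combined protocol and SAP*

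**What the plan says.** The fMRI paragraph of the Statistical Analysis Plan for Aim 1 builds task-versus-rest contrasts separately for IG and EG. Those "derived in each subject will be submitted to a second-level, random-effects analysis with subject as a random factor", and the resulting group maps are thresholded at p<.05 with FDR correction. The plan then states: "These activation maps will be used to define circuitry for IG and EG foot-tapping".

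Percent signal change for each participant "will be extracted from the centers of gravity of the activated regions" and is "submitted to hierarchical regression analyses to determine whether they correlate with behavioral measures". The same paragraph closes with "The primary outcome measure will be average percent signal change", for the purpose of telling IG circuits from EG circuits in people with and without PD. The Power Analysis for Specific Aim 1 assigns that purpose to an ANOVA.

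Hypothesis 1 in the Objectives names the structures in advance, for example "STC (posterosuperior putamen, ventral anterolateral thalamus, rostral supplementary motor area, primary motor cortex". The Specific Aim 1 rationale repeats and justifies the list. No coordinates or masks are fixed, and no independent localiser or leave-one-out selection is described. The plan does not say whether the second-level maps pool PD and controls, or whether both tasks are read at the same locations.

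**The concern.** A region enters the analysis, and its centre is placed, because it passed the threshold for one task in these participants. Chance noise helped it pass. Reading that task's signal at that place in the same data keeps the helpful noise; reading the other task there keeps only the part of the noise that the two tasks share. A difference between tasks can then appear where none exists.

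The tilt makes IG look stronger at IG locations and EG stronger at EG locations. That is the dissociation Hypothesis 1 predicts for controls, so the primary imaging outcome could report task-specific circuits that the selection step helped to create. The same mechanism would act on PD versus control if a map from one group alone supplied the locations.

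**Working it through.** **1. The plan's own figure.** Inputs from the Power Analysis for Specific Aim 1: 20 per group, f = 0.45, alpha .05, F(1,38) = 4.098. Noncentrality is f² × N = 0.45² × 40 = 8.1. The critical value is 4.098, as stated, and power is 0.792 against the stated 0.80, so the figure reproduces. It concerns a between-subject contrast. The plan gives no expected size for task-versus-rest activation or for IG versus EG.

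**2. Mechanism.** Let b be the noise inflation, in between-subject SDs, of the task whose map chose the location, and ρ the within-person IG-EG correlation. The other task inherits ρb, so the spurious difference is (1 − ρ)b. With N participants the paired test has noncentrality (1 − ρ)b / √(2(1 − ρ)) × √N.

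**3. Null simulation under the plan's rule.**
- From the documents: 20 + 20 participants, 3 mm voxels, 5 mm smoothing, FDR .05, centre of gravity.
- Assumed: one active region in a 12×12×12 volume, largest cluster used, equal true activation in both tasks and both groups, peak d of 0.3, 0.5 or 0.8, and ρ of 0.3 or 0.7. There were 400 runs per setting.

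Locations from the IG map pooled over groups, nominal 5%:

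| d | ρ | IG vs EG false positives | Spurious difference (SD) | Network-by-task false positives |
|---|---|---|---|---|
| 0.3 | 0.3 | 22.5% | 0.23 | 51% |
| 0.3 | 0.7 | 13.6% | 0.11 | 26% |
| 0.5 | 0.3 | 5.0% | 0.047 | 6.2% |
| 0.5 | 0.7 | 4.0% | 0.021 | 4.3% |
| 0.8 | 0.3 | 2.5% | 0.040 | 3.7% |
| 0.8 | 0.7 | 6.0% | 0.004 | 4.3% |

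The network-by-task column compares IG-map with EG-map locations.

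**4. Hand check of the first two rows.**
- ρ = 0.3: 0.23 / √1.4 × √40 = 0.23 / 1.183 × 6.325 = 1.23. A noncentral t with 39 df rejects 22.4% of the time, against 22.5% simulated.
- ρ = 0.7: 0.11 / √0.6 × √40 = 0.11 / 0.775 × 6.325 = 0.90, giving 14.2% against 13.6%.
- Implied inflation b is 0.23 / 0.7 = 0.33 and 0.11 / 0.3 = 0.37 SD, similar in both rows, as the mechanism predicts.

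**5. Range.** A separate null simulation with the same threshold and centre-of-gravity rule, covering weak or focal activation, widened the IG-versus-EG range to about 14-45% at d = 0.3 and about 3-18% at d = 0.5. It gave about 4-6% at d = 0.8.

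**6. PD versus control.**
- Maps pooled over equal groups: 3.3-7.5% false positives, spurious difference at most 0.04 SD.
- PD-only map: 57-61% at d = 0.3 (about 110 usable runs in one setting), 25-28% at d = 0.5, and 4.5-5.5% at d = 0.8.
- Hand check at d = 0.5: 0.406 / √(2/20) = 1.28, giving 24.0% with 38 df.

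**7. Remedies in the step 3 simulation.** An independent localiser gave 4.0-7.7% for both contrasts. One location set from the pooled average of IG and EG gave 3.3-7.2%. Monte Carlo error is about 1.1-1.3 points, so both are close to nominal.

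**The case against.** The strongest reply is that the extraction sentence feeds the regression on tapping behaviour, not the ANOVA. Part of that stands: choosing locations on task versus rest does not by itself bias a correlation with behaviour, and the link to the Aim 1 ANOVA is not spelled out. But the paragraph describes only one way of obtaining percent signal change and then names percent signal change as the primary outcome. The Aim 2 activation plan, said to follow Aim 1, uses values "extracted from the centers of gravity of the activated regions" and sends percent signal change to a repeated-measures ANOVA. Using the same values in Aim 1 is the natural reading.

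A second reply is that the structures are named in advance. This limits which regions can be claimed, but the point read within each structure is still data-driven.

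Several stronger readings are tempting and are not supported:

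- *PD versus control is biased.* With maps pooled over equal groups it is not materially so, and the powered F(1,38) contrast is between subjects. Per-group maps are possible but not stated.
- *The inflation is a known percentage.* It runs from marked to nil with activation strength and extent, neither of which the documents give.
- *The bias always helps the hypothesis.* In PD, IG tapping is predicted to engage both circuits, so a tilt toward EG at EG locations works against part of the prediction.
- *The Aim 2 activation analysis is shown to be biased.* Its contrast is group by time, its named primary outcome is a set of statistical maps, and no calculation here covers it.

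**Conclusion.** The point holds for the comparison of tasks. Where each task's own map supplies the location, IG versus EG and the network-by-task contrast are circular as the rule is written. For PD versus control there is an unresolved choice, harmless if maps are pooled over equal groups and potentially serious if they are made per group.

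The direction for the task comparison is firm; the size is not. It rests on assumed activation strength, activation extent and IG-EG correlation. Inflation is well above 5% for weak or focal activation and close to nominal for strong, compact activation. Because the documents state no expected activation strength, the plan cannot show that it lies in the safe range.

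**What to change.** For the Aim 1 comparison of tasks and groups, state that percent signal change is extracted from one common set of locations used for both tasks and both groups. Any of these would serve:

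- a single map averaging IG and EG over PD and controls with equal weight;
- leave-one-participant-out selection of the locations;
- a-priori anatomical masks of the structures already named in Hypothesis 1 and the Specific Aim 1 rationale.

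Keep the task-specific FDR maps as descriptive results, and state that the ANOVA uses these common-location values and which of its contrasts is primary.

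The cost is a few sentences in the SAP and a little more analysis work, with no new data. Anatomical masks may dilute a small focal activation; the averaged map or leave-one-out selection is the alternative if that is a worry.

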For ~20 minutes, participants will perform IG and EG sequences of foot-tapping movements inside the scanner using established methods . As such, the task will involve unilateral ankle dorsiflexion, to a maximum of 30° in a wooden apparatus with movements blocked by IG or EG condition. Participants will be provided foam padding and towels to restrain head motion. Participants’ knees will be flexed to approximately 135° with a soft roll under the knees. An assistant will verify task performance timing and amplitude, as well as monitor for synkinesia from the other limb. If the patient is unable to keep the other limb still, the data will be excluded. Based on pilot scans that we recently collected in 15 individuals with stage II and III PD, we expect 20% attrition for excessive head movement. However, these participants were scanned while ON meds, which generally increases the presence of dyskinesia. Because we will a) test participants OFF meds, b) screen for excessive head and lower limb tremor, and c) target recruitment in order to account for 20% attrition, we expect to retain a sample size that will allow us to detect effects and make meaningful comparisons. Ankle range of motion will be recorded with an MR-compatible potentiometer and amplitude will be averaged over each condition. Absolute timing error will be determined by the potentiometer also, by comparing the timing of every other change in acceleration, with the ideal timing sequence. Thus, the time course of changes in acceleration will be effectively considered the timing of the participants’ taps. Error will be averaged from the accumulated absolute value of the tapping errors which either over- or under-shoot the ideal timing. Tapping will occur at a frequency of 0.5 - 2 Hz, *IRB 60613 Motor Training in PD*

Activation paradigm: In 30 s EG blocks, participants will tap their feet in response to externally provided auditory cues. In 30s IG blocks, participants will tap their feet in pre-learned rhythms. 21 s of rest will occur between IG and EG blocks. There will be 5 blocks per condition

given that individuals with PD demonstrate marked tapping performance deterioration above 2 Hz, in terms of increased movement rate, decreased amplitude and loss of movement phase.

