### **Intervention: IG and EG training in adapted tango classes for participants with PD**

**Dosage:** Participants shall receive 1.5 hours of progressive IG or EG adapted tango dance, or BC, a health education class 2 days/week for 12 weeks, with a goal of 20 completed lessons, in the Atlanta

VA Rehabilitation R&D Center's 41 ft x 34 ft Movement Studies Lab. To examine neural circuitry in conjunction with intervention, an effective dose of that intervention must be used, i.e., one with demonstrated improvements in mobility and balance via outcome measures of interest. Twenty sessions were used previously and were effective at improving mobility (See preliminary studies). We expect 20 lessons over 12 weeks will provide enough therapy for both functional improvements to manifest as well as neurological changes to have occurred, because one month after training cessation, observations revealed maintained gains in the absence of treatment. Thus, all participants must complete all 20 lessons to include their data in analyses. Participants will have ample opportunity to complete 20 lessons: there will be 4 lessons offered per week for 12 weeks (48 total sessions). If necessary, make up sessions will be offered. To date, we have experienced ~15 % attrition. Notably, in a recent pilot study in Atlanta examining intensive tango, there was 0% attrition.

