## **6. Participant Selection**

### **Recruitment and Informed consent:**

**Recruitment:** We will recruit 140 adults aged 40-85, with PD stages II-III and 24 age-matched controls. Individuals without PD (controls) will be recruited from the Atlanta VAMC RR&D CoE's registry, the VA's VINCI database, as well as at senior living communities with whom the PI has a relationship. All patient information will be stored on VA secure servers (room 3A 105) of the Atlanta VA Medical Center. Only authorized study team members will have access to this information because it will be stored on a private directory with limited access and password locked file.

We will request a partial HIPAA waiver to identify potential participants for recruitment purposes from IRB and related approvals from the local VA R&D committees. We will then obtain a list from the VA Movement Disorders clinic including patients likely to have a PD diagnosis, and send them a letter, with the director's signature informing them about the study. Drs. [name] and [name], among others, will assist. A follow-up call will be placed within two weeks of the veteran likely having received the letter. A telephone screen will determine eligibility for participating in fMRI. Also, study fliers will be posted in the medical center and a PowerPoint slide ad will be broadcast throughout the medical center closed circuit TV system, such that veteran self-referrals are possible. To aid recruitment efforts, the PI will initiate meetings with community providers to explain the research goals, and request them to send a letter describing the study to patients who may qualify and have interest. The PI and staff will also visit PD community support and educational groups to present information to potential participants. Specifically, the PI will present information about the study to potential subjects at the 10+ support groups meeting monthly, organized by the GA chapter of the American Parkinson Disease Association and other PD organizations. The PI will also draft information about the trial to be included in the APDA and other PD organizations' newsletters and informational material, as well as the Michael J Fox foxfinder website for clinical trials in PD.

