## 7. Statistical Analyses

**Power Analysis for Specific Aim 1:** We anticipate that 20 participants in each group (total n=40) will be necessary to detect an adequate effect size at 80% power based on studies conducted to determine reasonable sample sizes for fMRI studies. Twenty-four participants per group will be recruited to accommodate 20% attrition. Analysis of variance (ANOVA) will be used to determine and distinguish circuits involved in IG and EG foot-tapping networks in participants with and without PD. The ANOVA will be sensitive to between subjects effect sizes of  $f=0.45$  ( $F_1, 38= 4.098$ ), with a power of 0.80 at  $\alpha=.05$ .

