**Hypothesis 1:** Power calculations for Aim 2 are based upon an assumed 4-point improvement and effect sizes  $> 0.8$  on the BBS after 12 weeks of adapted tango, which was attained previously (see Preliminary Studies), and the minimal detectable change on the BBS in parkinsonism is 2.84 points. Therefore, with a total sample size of 63 participants (21 participants in each of 3 groups: IG, EG, and BC) a repeated measures (RM) ANOVA with 3 levels of repeat will be sensitive to between-within interaction main effect size of  $f(v) = 0.44$  ( $F_{4,114} = 2.45$ ) with a power of 0.80 at  $\alpha=.05$ . Post hoc sensitivity to effects between groups will be  $d = 0.90$ , and within groups,  $d_z = 0.65$ . To reflect an anticipated 20% attrition, we will recruit an additional 4 participants per group. Thus we will recruit 25 participants per group, for a total of 75 individuals with PD recruited for Aim 2. **Hypothesis 2:** 25 participants per group will be sufficient to detect effects for the imaging (activation and resting state) components of Aim 2 as well, based on studies conducted to determine reasonable sample sizes for fMRI studies, that demonstrate at least 20 participants in each group are necessary. **Hypothesis 3:** Differences in RSfc have been noted between different groups of individuals with PD in sample sizes of 16 per group; therefore, with 25 individuals per group, we will be able to detect differences between groups.

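### The Aim 2 power statement is for 63 analysed participants, but its own 20% attrition and its printed error df both give 60; Aim 1 makes the same attrition slip

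*Combined protocol and SAP*

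**What the plan says.** **Aim 2** (section 7, Power Analyses for Aim 2, Hypothesis 1). Power of 0.80 at alpha 0.05 is claimed "with a total sample size of 63 participants (21 participants in each of 3 groups: IG, EG, and BC"). The test is a repeated measures ANOVA with three time points, and the interaction effect is f(V) = 0.44, printed with F(4,114) = 2.45. Post hoc sensitivity is given as d = 0.90 between groups and dz = 0.65 within groups. For losses the plan says "To reflect an anticipated 20% attrition, we will recruit an additional 4 participants per group", and concludes that "we will recruit 25 participants per group, for a total of 75 individuals with PD recruited for Aim 2".

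**Aim 1** (section 7, Power Analysis for Specific Aim 1). "We anticipate that 20 participants in each group (total n=40) will be necessary", with f = 0.45 and F(1,38) = 4.098. Then: "Twenty-four participants per group will be recruited to accommodate 20% attrition".

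**Elsewhere.**
- The Aim 1 experimental plan bases its allowance on pilot scans of 15 people with PD: "we expect 20% attrition for excessive head movement".
- The Dosage paragraph reports, of earlier training studies, "To date, we have experienced ~15 % attrition". It also limits the analysis to people who complete all 20 lessons.
- Section 6 gives a different recruitment total: "We will recruit 140 adults aged 40-85, with PD stages II-III and 24 age-matched controls".

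**The concern.** Attrition is a fraction of those recruited. To end with n analysed at 20% loss, one recruits n/0.8. The plan appears to have added 20% of n instead, which falls short. In Aim 2 the printed error df does not match the stated sample size either.

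This is the power statement for the BBS, the outcome on which Aim 2 is powered. A reader who tries to check it meets two different analysed totals, 63 and 60, and cannot tell which one the design rests on.

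**Working it through.** **Error df, Aim 2.** Statistical Analysis Plan for Aim 2 specifies 3 groups x 3 times. The interaction has (3 - 1)(3 - 1) = 4 numerator df and (N - 3) x (3 - 1) error df. The multivariate (Pillai) form gives the same error df.
- N = 63: (63 - 3) x 2 = 120, critical F 2.447
- N = 60: (60 - 3) x 2 = 114, critical F 2.451

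Both critical values print as 2.45, so only the df shows the mismatch. This step uses no effect-size convention.

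**Attrition.**

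| | Aim 2, per group | Aim 1, per group |
|---|---|---|
| Stated number for analysis | 21 | 20 |
| Recruited | 25 | 24 |
| Left after 20% loss | 25 x 0.8 = 20 | 24 x 0.8 = 19.2 |
| Loss the allowance really covers | 1 - 21/25 = 16% | 1 - 20/24 = 16.7% |
| n x 1.2 | 25.2 | 24 |
| n / 0.8 | 26.25 | 25 |

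Both recruitment figures match n x 1.2. For Aim 1, the 20% comes from pilot scans as a loss among people scanned, so it applies to those recruited.

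**Reproducing the stated Aim 2 power.** The plan does not say how f(V) enters the noncentrality parameter λ, so three conventions are shown. Power is from the noncentral F at f = 0.44 and alpha 0.05.

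| Convention (assumed) | Power, N = 63 | Power, N = 60 | f for 80%, N = 63 | f for 80%, N = 60 |
|---|---|---|---|---|
| λ = N f² (12.20; 11.62) | 79.2% | 76.8% | 0.444 | 0.455 |
| λ = (N - 3) f² | 76.9% | 74.4% | 0.455 | 0.467 |
| λ = 2N f² | 98.4% | 97.9% | 0.314 | 0.322 |

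With λ = N f², the stated 0.80 is reproduced at N = 63 to within a point. The difference between 63 and 60 is 2.4, 2.5 and 0.5 points in the three rows.

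**Post hoc comparisons** (two-sided t-tests at 0.05, assumed).
- Between groups, d = 0.90: power 81.2% at 21 per group and 79.2% at 20. The d for 80% power is 0.886 and 0.909.
- Within groups, dz = 0.65: power 80.9% at 21 and 78.7% at 20. The dz for 80% power is 0.643 and 0.660.

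The printed 0.90 and 0.65 lie between the values for 21 and 20, so they do not show which n was used.

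**Aim 1** (λ = N f², f = 0.45).
- N = 40: critical F(1,38) = 4.098, as printed; power 79.2%.
- N = 38 (19 per group): critical F(1,36) = 4.113; power 77.0%; f for 80% is 0.467.

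The Aim 1 df agree with its N, so only its attrition step is off.

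**The case against.** **The power itself reproduces.** With λ = N f², the f for 80% power is 0.444 at N = 63, which prints as 0.44, and 0.455 at N = 60. The same convention gives 0.4546 for Aim 1 at N = 40, printed as 0.45. This suggests that f(V) was computed at 63 and that the df of 114 is the slip. It is a fair pointer but not proof: the documents name no convention, d and dz are uninformative, and the 20% attrition points to 60. The 98% row is also hard to square with a stated power of 0.80. Setting it aside leaves a difference of about 2.4 to 2.5 points.

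**Losses may be lower than 20%.** At the roughly 15% reported under Dosage, 25 x 0.85 = 21.25, so 21 per group would remain. The Aim 1 experimental plan also gives reasons to expect fewer scan losses. Neither changes the fact that the power section plans on 20%, and neither explains 114 df.

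**Hypothesis 2 is unaffected.** Its imaging comparison asks for at least 20 per group, which 25 x 0.8 meets exactly. That stands.

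**The target may be larger.** If more than 75 of the 140 participants with PD in section 6 are randomised, the Aim 2 shortfall may not arise. But the power section says 75 for Aim 2, and the df mismatch would remain.

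**Conclusion.** The concern holds and is minor. In Aim 2, 63 analysed, an error df of 114, and 25 recruited at 20% attrition are mutually inconsistent. In Aim 1, 24 recruited at 20% attrition does not leave the 20 per group described as necessary. These conclusions need only the stated design and the usual meaning of attrition as a share of those recruited.

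The shortfall is about one participant per group in each aim. For Aim 2 it costs 0.5 to 2.5 points of interaction power, depending on the assumed convention, and about 2 points in the post hoc tests. For Aim 1 it costs 2.2 points (79.2% to 77.0%). The documents do not settle which figure in the Aim 2 statement is the slip.

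**What to change.** **Aim 2:** make the analysed N, the df and the attrition agree, in one of two ways.
- (a) Restate at 60 analysed (20 per group) with F(4,114) = 2.45, d = 0.91 and dz = 0.66. Recompute f(V) under a named convention; it is 0.455 if λ = N f².
- (b) Keep 63, print F(4,120) = 2.45, and state that 25 per group covers 16% attrition.

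**Aim 1:** likewise.
- (a) Restate at 19 per group with F(1,36) = 4.11 and f = 0.47, and change the statement that 20 are necessary.
- (b) Keep 20, and state that 24 per group covers about 17% attrition.

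In the same edit, reconcile the 75 participants with PD in the power section with the 140 in section 6 (Recruitment, and Human Subjects Involvement and Characteristics).

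**Cost:** wording only, with no extra enrolment. Keeping both the analysed N and the 20% would instead need 27 per group for Aim 2 (26.25 rounded up; 81 - 75 = 6 more people) and 25 per group for Aim 1 (50 - 48 = 2 more). For so small a loss of power, the wording change is enough.
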